13. STATISTICAL ANALYSIS

Data will be analyzed in M0 and M1. It will be tested the data for normality and homogeneity of variance with the Shapiro Wilk and Levene's tests, respectively. Data analysis will be described according to the established purposes for this project (descriptive values: mean, standard deviation, range, % change) and comparisons of means will be used for all purposed

outcomes intra and inter groups. Baseline characteristics between groups will be evaluated with oneway ANOVA. Mixed between within subjects ANOVA will be conducted in a 2 (pre vs post ExT) design to assess efficiency of the program. When a significant interaction is observed, t tests, or Wilcoxon signed-rank tests will be used to determine where the interaction occurred.

M0 versus M1 will be compared to evaluate the changes in patients and trace the necessary timespan for such changes using General Linear Mixed Model Analysis for repeated measures with Tukey's posthoc procedure for the mean comparisons. Pearson product moment correlation coefficient or Spearman's rank correlation coefficient will be used to study the relationship between different variables by group and correlation coefficients will be compared between groups. Statistical significance will be set at an alpha level of 0.05. Other statistical procedures can be done.

Statistical analyses will be conducted using Statistical Package for the Social Sciences (SPSS) 22.0 (IBM SPSS Statistics, Chicago, IL, USA).

Data analysis will allow peer reviews publication, slide presentations and oral communications in national and international conferences, during year of 2018 and beginning of 2019 to present all the results of the project.

REFERENCES

1. R. Belardinelli, D. Georgiou, G. Cianci and A. Purcaro, *10-year exercise training in chronic heart failure: A randomized controlled trial*, J Am Coll Cardiol **60** (2012), no. 16, 1521-1528.
2. G. Loncar, S. Fülster, S. von Haehling and V. Popovic, *Metabolism and the heart: An overview of muscle, fat, and bone metabolism in heart failure*, Int J Cardiol **162** (2013), no. 2, 77-85.
3. J. Y. Tabet, P. Meurin, A. B. Driss, H. Weber, N. Renaud, A. Grosdemouge, F. Beauvais and A. Cohen-Solal, *Benefits of exercise training in chronic heart failure*, Arch Cardiovasc Dis **102** (2009), no. 10, 721-730.

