Study Protocol and Statistical Analysis Plan

EFFECTIVENESS OF COMBINED AEROBIC AND STRENGTH TRAINING IN ACUTE AND CHRONIC ADAPTATIONS IN PATIENTS WITH HEART FAILURE

Date: 19/10/2017

PROTOCOL

Title

Effectiveness of combined aerobic and strength training in acute and chronic adaptations in patients with heart failure

Participants

Patients with chronic heart failure (CHF) that underwent to a hospital-based cardiac rehabilitation (CR) program in the Lisbon district Hospitals will be recruited. The study will be performed in the Cardiovascular Rehabilitation Center of the University of Lisbon (CRECUL) at the Lisbon University Stadium (EUL). The participants will be randomized into one of the following exercise groups: A) combined exercise training with more aerobic training and less strength training (CAT); B) combined exercise training with more strength training and less aerobic training (CST); Inclusion criteria: CHF patients; receiving optimal medical therapy for CHF (including an angiotensin-converting enzyme inhibitor or an angiotensin receptor blocker and a beta-blocker unless a contraindication is evident) with a stable condition for more than 1 month (no hospitalization for heart failure (HF), no change in medication, and no change in New York Heart Association (NYHA) functional class. Exclusion criteria: if they are younger than 18 years or are unable to sign informed consent; unstable angina pectoris; and orthopedic or neurological limitations to exercise. Patients will be stratified (by age and etiology) and randomized consecutively to CAT or CST in the beginning of the exercise at community. There will be 2 assessment moments (M): M0) before starting the exercise training (ExT) program (baseline) and M1) 3 month after starting the ExT.

Sample size was calculated (G-Power, Version3.1.3) assuming a difference in carotid intima-media thickness (IMT) between groups of 5% to be a clinical important difference with a SD of 0.16, $\alpha=0.05$, $1-\beta=0.95$ and an expected dropout rate of 26%. The calculations yielded a total minimum sample size of 28 participants (14 in each group).

Recruitment

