This research project is going to employ state of the art methods focusing peripheral adaptations analysis in both groups namely in echocardiography variables, cardiopulmonary exercise testing, arterial stiffness, functional physical fitness, QoL and body composition in 2 distinguished moments: M1) baseline and M2) 3 month.

Plan and Methods

This project will assess the acute and chronic effects in central and peripheral adaptations of a combined training to patients with CHF would address a number of important breaches in scientific knowledge with potential clinical benefits.

STUDY DESIGN

A longitudinal randomized control trial (RCT) research design using two distinct ExT prescriptions (CAT and CST) will be applied in CHF patients. All the same assessments will be done in two moments: M0 - baseline and M1 - 3 months after starting the ExT. The patients will be randomized into either one of the two ExT group.

Recruitment and screening will last 9 months (September 2017 to May 2018) and the patient assessment will last until August 2018. It is expected to finish the project with peer-review redaction submitted and/or accepted in December 2018 (time line attached).

The following assessments on the 4 moments will be performed at the Pulido Valente Hospital, FMH-UL and Academia de Fitness at EUL: Echocardiogram (Echo) (MyLab Alpha, ESAOTE);

cardiopulmonary exercise test (CPET) (Ergostik, Geratherm Respiratory GmbH, Bad Kissingen); arterial stiffness - Complior Analyse (ALAM Medical); Intima-media thickness - ultrasound (ESAOTE MyLanOne); body composition - dual energy radiographic absorptiometry (DXA, Hologic Explorer-W); functional physical fitness - Fullerton Functional Fitness Test; isometric strength – portable hand dynamometer JAMAR plus digital (Sammons Preston); maximal strength – 1RM and QoL questionnaire.

All assessment moments will be done in 5 days:

Day 1 – Echo will be performed at the Pulido Valente Hospital;

Day 2 and 3 – during one day and time of the ExT session at the EUL, the patient will perform the functional physical fitness tests; maximal strength; isometric strength and QoL questionnaire. In other day the investigators will perform the arterial stiffness and the IMT before the session in rest and after the ExT;

Day 4 – In FMH, the CPET and dual energy radiographic absorptiometry (DXA) exam.

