7. FUNCTIONAL PHYSICAL FITNESS TESTS

The functional physical fitness tests are a simple, reproducible, readily available tool frequently employed to assess submaximal functional capacity and evaluate the response to intervention. The six minute walking test (6MWT) will be performed indoors, along a long flat, straight, enclosed 20-meter corridor with a hard surface that is seldom. Patients will be instructed to walk at their own pace according to their tolerance to exercise for 6 minutes, with rest stops as needed. The final result will be the distance in meters covered in the 6 minutes. Total distance during the test will be recorded. Because the body weight of patients directly affect the energy and work required to walk, it will be used the body weight-walking distance (body weight × walking distance) to assess the walking capacity of subjects. The aim of the 6MWT is to assess aerobic endurance. The 30-second chair stand, assesses the lower body strength, needed for numerous tasks such as climbing stairs or walking. Patients will be instructed to sit and stand as faster as they can in 30 seconds with arms folded across chest. The 8-foot (2.44 meters) up and go test evaluates the agility/dynamic balance, which is important in tasks that require quick maneuvering. It will be evaluated the time in seconds that the participant needed to get up, walk the distance of 2.44 meters and return to the initial position. For the flexibility, it will be assessed in both upper and lower body. The chair sit-and-reach aim to assess the lower body flexibility from a sitting position at front of a chair with the leg extended and hands reaching toward the toes, the number of cm between extended fingers and tip toes (+ or -) will be measured. To assess the upper body (shoulder) flexibility, it will be used the back scratch test with one hand reaching over the shoulder and one up the middle of the back, it will be taken the number of cm between extended middle fingers (+ or -).

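### Percent change is listed as a summary with no outcome excluded, but the two flexibility tests are signed cm scores, on which it can be wrong in sign, very large or undefined

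*Combined protocol and SAP*

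**What the plan says.** Section 13 describes the data with "descriptive values: mean, standard deviation, range, % change". The same sentence goes on to apply comparisons of means to all proposed outcomes, "outcomes intra and inter groups". It gives no formula for % change. It does not say whether the figure is computed per patient and averaged or taken from arm means, and it exempts no variable.

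Section 7 describes the two flexibility tests. For the chair sit-and-reach, "the number of cm between extended fingers and tip toes (+ or -) will be measured". The back scratch entry reads "it will be taken the number of cm between extended middle fingers (+ or" and closes with the minus sign. Neither entry says which direction is plus.

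Both tests belong to the outcome set. The Study Design section lists "functional physical fitness - Fullerton Functional Fitness Test" among the assessments and sets the two time points as "M0 - baseline and M1 - 3 months after starting the ExT".

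**The concern.** Percent change has a stable meaning only on a scale that is strictly positive with a true zero. On the two flexibility tests, zero means only that the fingers just meet the target, and patients can score on either side of it. Dividing by such a baseline can reverse the sign of an improvement, inflate it without limit, or leave it undefined.

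If the list in section 13 is applied to every outcome, a published table could show better flexibility as a loss. It could also show CAT and CST as far apart when both gained the same number of cm. Arms are small, at 14 per group, so one near-zero baseline can dominate an arm's average percentage.

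**Working it through.** The plan states no figure that rests on this summary, so there is nothing of its own to reproduce. The check is arithmetic, followed by an illustration under stated assumptions.

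**1. Same gain, different baselines.** Formula (assumed, since none is given): % change = 100 × (M1 − M0)/M0. Assumed direction: plus means reaching past the target.

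| M0 (cm) | M1 (cm) | Change (cm) | Dividing by M0 | Dividing by \|M0\| |
|---|---|---|---|---|
| −10 | −5 | +5 | −50% | +50% |
| −1 | +4 | +5 | −500% | +500% |
| −0.5 | +4.5 | +5 | −1000% | +1000% |
| 0 | +5 | +5 | undefined | undefined |
| +1 | +6 | +5 | +500% | +500% |
| +5 | +10 | +5 | +100% | +100% |
| +10 | +15 | +5 | +50% | +50% |
| −5 | −10 | −5 | +100% | −100% |

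The last row is a worsening reported as +100%. The absolute denominator corrects the sign but leaves the inflation near zero and the gap at zero.

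**2. Opposite scoring direction.** If plus meant falling short, improvement would be a fall in the score. From +10 to +5 the result is −50%; from −5 to −10, also an improvement, it is +100%. The sign is inconsistent under either convention.

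**3. Arm means instead of patient values.** Arm means of −10 and −7 cm give 100 × 3/(−10) = −30% for a 3 cm improvement. The choice of formula also matters. Take 11 made-up baselines of −12, −8, −5, −3, −1, 0.5, 1, 2, 4, 6 and 8 cm, each improved by 3 cm. The mean baseline is −7.5/11 = −0.68 cm, so the change in means is 100 × 3/(−0.68) = −440%. The average of the 11 individual percentages is 690/11 = +63%.

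**4. How often, under assumptions.** Assume normal baselines with SD 10 cm, a gain of exactly 3 cm in everyone, and 14 per arm. Dividing by M0:
- an improving patient's figure is negative when M0 < 0, with probability Φ(−mean/10);
- it exceeds 100% in size when |M0| < 3, with probability Φ((3 − mean)/10) − Φ((−3 − mean)/10);
- an arm's change in means is negative with probability Φ(−mean × √14/10).

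| Assumed baseline mean (cm) | Patients with negative % | Patients above 100% in size | Arms with negative % (change in means) |
|---|---|---|---|
| −10 | 84% | 15% | about 100% |
| −5 | 69% | 21% | 97% |
| 0 | 50% | 24% | 50% |
| +5 | 31% | 21% | 3% |
| +10 | 16% | 15% | about 0% |

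**5. Averaging individual percentages.** The formulas above do not cover this case, so it was simulated with the same SD and gain, added noise of SD 2 cm and readings to 0.5 cm, with zero baselines dropped. The arm average was negative in about 78%, 65%, 50% and 35% of arms at baseline means of −10, −5, 0 and +5 cm. The mean change in cm was essentially never negative. At a baseline mean of −5 cm, the 5th to 95th percentiles of the arm average ran from about −89% to +63% for the same true gain.

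**6. Undefined values.** With readings to 0.5 cm, a baseline is recorded as exactly 0 with probability of about 1.2% (mean ±10 cm) to 2.0% (mean 0). Among 28 patients, the chance of at least one is 1 − (1 − 0.012)^28 = 29% to 1 − (1 − 0.020)^28 = 43%. The plan has no rule for that patient.

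**The case against.** The strongest reply concerns scope and consequence.

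- **Scope.** In the section 13 sentence, all proposed outcomes most directly governs the comparisons of means. Percent change sits in a bracketed list of descriptive values, and the flexibility tests are not named. A reader might infer that the plan orders % change for every variable; the text does not say so. It does not exclude any variable either, and that part of the point stands.
- **Inference.** A reader might infer that the treatment comparison is compromised. The documents do not support this. The mixed ANOVA, the follow-up t or Wilcoxon tests and the mixed model are not said to be run on % change, and a scale that crosses zero poses no difficulty for them in cm.
- **Company in the table.** Mean, SD and range are listed beside % change, so a reader shown −10 and −7 cm can see the direction. This softens the harm but does not make the percentage correct.
- **Assumptions.** The direction of plus and the denominator are not stated. Zero-crossing does not depend on either, as steps 1 and 2 show. The frequencies do depend on the assumed baselines, and fall as baselines move above zero.
- **Weight.** These are two outcomes among many. The sample size rests on carotid IMT, and section 11 standardises the warm-up and cool-down, where the stretching takes place, across both groups.

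**Conclusion.** The point holds and is minor. For chair sit-and-reach and back scratch, % change can have the wrong sign when the baseline is negative, be very large when it is near zero, and not exist when it is exactly zero. That is certain arithmetic for the usual M0 denominator with plus meaning past the target. With |M0|, only the sign problem goes away.

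It would be too strong to say that every improving patient or arm gets a misleading figure. A clearly positive baseline gives an ordinary positive percentage.

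How often the problem would appear cannot be taken from the documents, which contain no flexibility data. Under the assumed SD of 10 cm and gain of 3 cm, the share of improving patients with a negative figure runs from 16% to 84% across baseline means of +10 to −10 cm. What is affected is the descriptive reporting of two outcomes that did not drive the sample size, not the planned tests.

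**What to change.** In section 13:
- report chair sit-and-reach and back scratch as M1 − M0 in cm, with the SD by arm and the CAT − CST difference in cm;
- state which direction of the score is better (in section 7 or section 13);
- limit % change to strictly positive ratio-scale outcomes such as cIMT, PWV, VO2peak and 1RM, and give its formula, including whether it is computed per patient or from arm means.

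After this change, a 5 cm gain is reported as 5 cm from any baseline, including zero. The change takes a sentence or two of text, with no new data, no extra patients and no change to any test. The only loss is a common percentage unit across the fitness tests.

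### The between-arm test in section 13 is valid but fixes the M0 slope at 1; a prespecified ANCOVA on M0 would be a cheap, modest precision improvement for most plausible M0–M1 correlations

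*Combined protocol and SAP*

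**What the plan says.** Section 13 (Statistical Analysis) gives the main comparison as "Mixed between within subjects ANOVA will be conducted in a 2 (pre vs post ExT) design to assess efficiency of the program", followed by: "When a significant interaction is observed, t tests, or Wilcoxon signed-rank tests will be used to determine where the interaction occurred". A general linear mixed model is added, in which "M0 versus M1 will be compared to evaluate the changes in patients". Baseline enters otherwise only as a comparison of the arms: "Baseline characteristics between groups will be evaluated with oneway ANOVA". No covariate is named for any model, and the closing allowance, "Other statistical procedures can be done", prespecifies none.

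The Participants section of the protocol says "Patients will be stratified (by age and etiology) and randomized consecutively to CAT or CST". It does not give the number of levels of either factor. It sizes the trial on carotid IMT, taking a difference "between groups of 5% to be a clinical important difference with a SD of 0.16", 95% power, alpha 0.05 and "an expected dropout rate of 26" (per cent), for 28 patients, 14 per arm. Study Design sets two assessments, M0 and M1 at three months.

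**The concern.** M0 is measured on everyone for each outcome, and age and etiology were thought important enough to stratify on. The planned test uses M0 only by subtracting it in full and does not use the other two at all. If the M0–M1 correlation for an outcome is low or moderate, full subtraction adds noise.

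With about 20 patients expected to be evaluable, interval width is the main limit on what the trial can say about CAT versus CST. The plan applies the same test to all outcomes (CPET, stiffness, IMT, body composition, strength, quality of life), and a slope of 1 is unlikely to suit all of them. Leaving adjustment open, next to a baseline comparison of the arms, also invites a choice of covariates after the data are seen.

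**Working it through.** **Inputs.** From the documents: two arms, two visits, 14 per arm, 26% dropout, difference 5% (read as 0.05), SD 0.16. Evaluable: 14 × 0.74 = 10.4 per arm, so 10 per arm, N = 20. Assumed, because the documents are silent: the M0–M1 correlation ρ (0.3 to 0.95), the SD ratio k = SD(M1)/SD(M0), and the prognostic value of age and etiology.

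**1. The plan's own figure.** d = 0.05/0.16 = 0.3125. A plain two-group comparison needs 2 × (1.960 + 1.645)² / 0.3125² = 267 per arm, so 28 in total is not reproduced. A repeated-measures formula reaches it only with an unstated correlation. With f = 0.156, ρ is about 0.90 for 28 analysed, or 0.93 for 20. With f = 0.3125, it is about 0.61 or 0.73. That gap is a separate matter, but it shows how uncertain ρ is.

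**2. What the planned test is.** With two groups, two visits and complete data, the interaction F equals the squared t on M1 − M0. A numerical check gave 1.2394 both ways.

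**3. ANCOVA on M0 alone.** In units of the M0 variance, the change score has variance 1 + k² − 2ρk, and ANCOVA has k²(1 − ρ²). The difference is (1 − ρk)², never negative. ANCOVA's only cost is estimating the slope: a factor (N − 3)/(N − 4) = 17/16 in variance and one df. With k = 1 the variance ratio is (1 + ρ)/2, so

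CI width ratio = √[(1 + ρ)/2 × 17/16] × t₁₇/t₁₈, with t₁₇/t₁₈ = 2.110/2.101 = 1.004.

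| ρ | (1+ρ)/2 | × 17/16 | width ratio |
|---|---|---|---|
| 0.3 | 0.650 | 0.691 | 0.83 |
| 0.5 | 0.750 | 0.797 | 0.90 |
| 0.7 | 0.850 | 0.903 | 0.95 |
| 0.8 | 0.900 | 0.956 | 0.98 |
| 0.9 | 0.950 | 1.009 | 1.01 |
| 0.95 | 0.975 | 1.036 | 1.02 |

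Break-even is near ρ = 0.87. Simulation with 10 evaluable per arm gives the same ratios.

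**4. Unequal SDs.** The loss is largest where ρk = 1. The ceiling there, for any ρ and k, is √(17/16) × 1.004 = 1.035. With k = 1.25 the variance ratio before the slope cost is 0.893 at ρ = 0.5 and 0.981 at 0.7, giving widths of 0.98 and 1.02. With k = 0.8 it is 0.571 and 0.628, giving √(0.571 × 17/16) × 1.004 = 0.78 and, likewise, 0.82.

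**5. Adding age (linear) and etiology (two classes).** Simulation: 20,000 replicates per cell, 14 per arm randomised, 4 per arm lost at random, k = 1. Balanced means strata identical between arms before dropout; unbalanced means strata independent of arm. Entries are widths relative to the planned test.

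| ρ | M0 only | uninformative, balanced | uninformative, unbalanced | 20% of residual, balanced | 20% of residual, unbalanced |
|---|---|---|---|---|---|
| 0.3 | 0.83 | 0.86 | 0.89 | 0.77 | 0.80 |
| 0.5 | 0.90 | 0.93 | 0.96 | 0.83 | 0.86 |
| 0.7 | 0.95 | 0.99 | 1.02 | 0.88 | 0.92 |
| 0.9 | 1.01 | 1.04 | 1.08 | 0.93 | 0.97 |
| 0.95 | 1.02 | 1.06 | 1.10 | 0.94 | 0.98 |

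Against M0 only, at ρ = 0.5:
- uninformative: 0.93/0.90 = 1.03 balanced, 0.96/0.90 = 1.07 unbalanced;
- informative: 0.83/0.90 = 0.92 balanced, 0.86/0.90 = 0.96 unbalanced.

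The other rows agree to within 0.01. With three levels per factor, uninformative and unbalanced, the width at ρ = 0.9 is 1.18 times that of the planned test.

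**6. Error rate and power.** If the stratifiers explain 20% of the residual variance, the planned test rejects under the null in 3.8–4.1% of runs with balance and 4.9–5.3% without. At d = 0.3125 its power is about 10% at ρ = 0.5 and 31% at 0.9. The largest power loss from M0-only ANCOVA, in a scan to ρ = 0.99, is 76.9% to 74.7%, at ρ = 0.97.

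**The case against.** The case for leaving the plan alone is that it contains no error. Both tests are valid, and which is narrower depends on ρ and the SD ratio, neither of which is given. For carotid IMT, the only outcome with a sample size, one reading of the 28 patients needs ρ of 0.90–0.93, where adjusting for M0 gains nothing. If M1 is more variable than M0, break-even comes earlier: with k = 1.25, M0-only ANCOVA already loses 2% at ρ = 0.7. ANCOVA also adds linearity and common-slope assumptions.

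Most of this stands, and it limits the claim to a modest gain. It does not reverse it, because the trade is lopsided: up to about 17% narrower in the equal-SD range, against a loss near 3% at worst. The other reading of the sample size (ρ of 0.61–0.73) favours ANCOVA. Slopes differing by arm did not raise the error rate beyond that of the planned test in simulations of the model with M0, age and etiology: at slopes of 0.1 and 0.9, null rejection was 6.1% planned and 5.7% ANCOVA.

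The objection succeeds fully against making the model with age and etiology the default. If those factors are uninformative, it is worse than M0 alone at every ρ examined. Its advantage rests on an assumed 20% that nothing in the documents supports or excludes.

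Pre versus post could also mean before and after a session. The sentence's stated aim, to assess the programme, favours M0 versus M1. On the other reading the M0–M1 comparison falls to the mixed model, which has no covariates either and gives the same interaction test with complete data.

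**Conclusion.** The point holds as one of precision, to be considered rather than required. For N = 20 and equal SDs, ANCOVA on M0 narrows the CI by about 17%, 10% and 5% at ρ = 0.3, 0.5 and 0.7 and widens it by 1–2% at 0.9–0.95. Break-even moves with the SD ratio, but the loss stays near 3% or less. Adding age and etiology is a secondary choice. It is about 7–8% narrower than M0 alone if they explain the assumed 20% and balance is achieved, but 3–4% wider (balanced) to 7–8% wider (unbalanced) if they do not predict the outcome.

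A reader might infer more, and the documents do not support it:
- That the planned test is invalid or inflates false positives. It is valid under randomisation. Omitting the stratifiers makes it somewhat conservative only if they are both balanced and prognostic.
- That stratified randomisation makes adjustment for age and etiology a sure gain. With their levels and prognostic value unknown, it can cost precision.
- That ANCOVA would rescue the stated 95% power. At the stated difference, power is far below 95% at low to moderate ρ with either method.

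**What to change.** In section 13, for each outcome's M0-to-M1 comparison:

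- Make the single between-arm test an ANCOVA of the resting (pre-session) M1 value on randomised group and the M0 value of the same outcome. Report the adjusted CAT–CST difference with its 95% CI. State separately how the acute pre/post-session measurements are analysed.
- For clearly non-normal residuals, name a rank version in advance. Allow logs only for strictly positive outcomes; the flexibility scores in section 7 can be negative.
- State that the general linear mixed model is descriptive and not a second between-arm test. The signed-rank test is paired, so it cannot compare the arms and should also be descriptive.
- If age and etiology are to be added because randomisation is stratified on them, fix the coding before analysis at one df each (for example age linear, etiology in two classes) and state the possible loss. Otherwise adjust for M0 alone.

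The cost is a few sentences of SAP text, with the same data and software. M0-only adjustment uses one of 18 residual df at 20 evaluable patients, and at most about 2 points of power were lost in the equal-SD scan. Adding age and etiology uses three df.

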Participants with established CHF after finishing in average a 3-month hospital based CR program at the Hospital will be invited and recruited to start a community based CR program at the EUL. The Clinical Director of the CR program at the Pulido de Valente Hospital and the Clinical Director of the community based CR program at the EUL, will make one of the connections to invite all the patients with the mentioned inclusion criteria to join the community based program. All patients will have access to informed consent (is attached the file of informed consent) where the entire project will be clearly explained.

Other forms to promote the recruitment in other Hospitals in the Lisbon district will be the distribution of a leaflet, with the contacts and brief information about the community based program. It will be presented and asked to each of the Clinical Director of the CR program at the Hospitals in Lisbon district the authorization to give to all the patients who completed the hospital based program the information leaflet.

All the information provided at the flyer will be online at the website of the University of Lisbon, Faculty of Human Kinetics – University of Lisbon (FMH-UL) and Faculty of Medicine – University of Lisbon.

INTRODUCTION

CHF is the major public health problem in the world [1], highly prevalent in older individuals and a major cause of disability, hospitalizations, morbidity and mortality [2]. Generally, CHF patients have reduced exercise capacity, with main symptoms of effort intolerance, early fatigue and breathlessness [3], also exhibiting increased peripheral and central chemosensitivity, and impaired sympathovagal balance with sympathetic activation (SA) predominance [4].

Understanding the oxidative metabolism and intracellular energy transfer in both skeletal and cardiac muscle, mechanisms of endothelial dysfunction, and the role of SA and inflammatory cytokines provide possible mechanistic explanations of the pathophysiologic factors involved in the development of exercise intolerance [5, 6]. It has been shown in CHF patients that increased arterial stiffness is associated with cardiovascular morbidity and mortality [7]. There are evidences that increased arterial stiffness predicts exercise intolerance in CHF patients [8].

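### Two assessments cannot show how long change takes, and without an untrained arm conclusions on effectiveness must rest on the CAT-versus-CST contrast

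*Combined protocol and SAP*

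**What the plan says.** **Schedule.** The Participants section sets two assessments: M0 before training and M1 three months after it starts. Section 12 (database and reports) uses the same pair, and section 13 opens with "Data will be analyzed in M0 and M1". The Study Design section also says two moments, but a later sentence there refers to four, with no timing given. The end of the Purpose section labels baseline and 3 months as M1 and M2 instead of M0 and M1.

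**Timing aim.** Section 13 states: "M0 versus M1 will be compared to evaluate the changes in patients and trace the necessary timespan for such changes". The method is a general linear mixed model for repeated measures "with Tukey's posthoc procedure for the mean comparisons".

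**Efficiency aim.** The same section states: "Mixed between within subjects ANOVA will be conducted in a 2 (pre vs post ExT) design to assess efficiency of the program". It continues: "When a significant interaction is observed, t tests, or Wilcoxon signed-rank tests will be used to determine where the interaction occurred". It also plans comparisons of means within and between groups for all outcomes.

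**Arms.** Both randomised arms, CAT and CST, do combined training. The Recruitment section describes the population as "Participants with established CHF after finishing in average a 3-month hospital based CR program". No arm goes without training.

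**The concern.** The first issue is a stated analysis aim that the design cannot deliver. In section 11 the strength load changes after week 2 and again after week 4, and interval work begins in week 2. When a response appears is therefore a natural question, but no outcome assessment is scheduled between M0 and M1. A published statement on the time needed for adaptation would have no data behind it.

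The second issue is smaller and concerns which result carries the conclusion. The ANOVA sentence names only the pre/post factor and ties it to the efficiency of the programme. Without an untrained arm, a time main effect or a within-arm change mixes training with time trend and with carry-over from the hospital programme. Randomisation supports a comparison of CAT with CST and nothing wider. No sentence says that this comparison, and not the time effect, will support the effectiveness claim.

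**Working it through.** **1. Can M0 and M1 trace timing?**

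Inputs: two time points, 0 and 3 months (Participants; Study Design; sections 12 and 13).

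- A straight line in time has 2 parameters, and two time points give a design matrix of rank 2, so it can be fitted. A quadratic has 3 parameters but the rank is still 2, so curvature cannot be estimated.
- Illustration, with time constants that are assumed and not in the documents: let the response follow 1 − exp(−t/τ), scaled to the same M0 and M1. The share of the 3-month change reached by month 1 is (1 − exp(−1/τ)) / (1 − exp(−3/τ)).

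| τ (months) | Share reached at month 1 |
|---|---|
| 0.3 | 96% |
| 1 | 67% |
| 3 | 45% |

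All three curves give identical data at M0 and M1.

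- With two time levels there is a single time contrast, so Tukey's procedure has nothing to adjust for that factor.

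**2. Could other planned data fill the gap?**

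- Arterial stiffness and IMT are measured at rest and after a session (Study Design; section 4). These describe change within one session, not across 3 months.
- Blood pressure is taken at every session and heart rate is monitored by telemetry (section 11). Section 13 does not analyse either across sessions, and neither would show the time course of IMT, peak oxygen uptake, strength or body composition.
- The reference to four moments gives no dates, contradicts the two moments in the same section, and is not carried into section 13.

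**3. What do the time effect and the interaction each test?**

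Let n be the number per arm, and measure change in units of its within-arm SD; df = 2n − 2, two-sided alpha 0.05 (the plan gives 0.05 but not the sidedness). In a 2 × 2 mixed ANOVA the interaction F equals the squared two-sample t on the change scores (0.476 = 0.476 on a test dataset). The interaction is therefore the CAT-versus-CST comparison of change. The time F equals the squared t on the mean change over both arms.

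Smallest observed value that reaches significance:

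- time effect: t / √(2n)
- interaction: t × √(2/n)

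The plan has 14 per arm. If the 26% dropout comes out of the 28, 14 × 0.74 = 10.4, so about 10 per arm remain.

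| n per arm | t | Time effect | Interaction |
|---|---|---|---|
| 14 | t(26) = 2.056 | 0.388 SD | 0.777 SD |
| 10 | t(18) = 2.101 | 0.470 SD | 0.940 SD |

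The factor of two holds for any equal two-arm pre/post design. The two thresholds also refer to different quantities, an average change and a difference between changes.

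**4. Illustration of a shared change not due to training**

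The documents give no size for such a change, so these shifts are assumed. With n = 14 and noncentrality d√(2n), shared shifts of 0.1, 0.2, 0.3, 0.5 and 0.8 SD of change make the time effect significant in about 8%, 17%, 33%, 72% and 98% of trials. The interaction stays at 5%, because a shift common to both arms cancels.

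**The case against.** The timing clause can fairly be called a stray phrase. Neither listed purpose mentions timing, and no outcome or sample-size input depends on it. That limits the harm but does not make the aim attainable. One could also answer that four moments are mentioned. With no dates, and with every other statement giving two, that reference cannot support a time course, but it should be settled before the clause is deleted.

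On the ANOVA, the defence is strong. A mixed between-within model needs a between-subject factor, and arm is the only candidate. The text promises within- and between-group comparisons, and the follow-up tests depend on a significant interaction. The first purpose ties effectiveness to different proportions of CAT and CST, and the sample size is stated for a difference between groups. A reader might infer from the wording that the trial will judge its programme by a pre/post test, or that the planned analysis is invalid. The documents do not support either inference: the wording allows the first but does not require it, and the interaction is a valid test of the randomised question.

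Some sources of spurious change are also limited. IMT is measured automatically, 1RM testing has four familiarisation sessions, and patients must be stable for more than a month. Time trend and carry-over remain. Because section 13 opens with M0 and M1, reading pre/post as those two assessments is natural; it needs stating mainly because acute measurements before and after a session also exist.

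**Conclusion.** The timespan clause is wrong as written. With no assessment between baseline and 3 months, the timing of change is not identifiable. This follows from the schedule alone and needs no assumed number; it rests only on two assessments being the intended schedule, which nearly all the text supports.

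The efficiency wording needs a limit on the conclusion, not a different kind of test. A time effect or within-arm change cannot be attributed to the programme; the CAT-versus-CST contrast can support a conclusion about the proportions of training. A reader might take the rejection rates of up to 98% as a measure of this trial's risk. They are not: they depend wholly on assumed shifts, fall to 8% at 0.1 SD, and should carry no weight in judging severity. Nor is the factor of two a defect particular to this plan.

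Overall this should be corrected before analysis. The timing clause is a clear error, and the second part is a clarification.

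**What to change.** 1. Reconcile the schedule first: two or four moments in Study Design, and the labels M0/M1 against M1/M2.
2. With two assessments confirmed, delete the clause about tracing the timespan. If more were intended, give their dates and an analysis that uses them.
3. Write the chronic-effect ANOVA as 2 (CAT, CST) × 2 (M0, M1). Describe the acute data from before and after a session as a separate analysis.
4. State that effectiveness conclusions rest on one contrast with its 95% CI: the baseline-adjusted CAT-versus-CST difference at M1, with the group-by-time interaction as support. The baseline value is already collected. The 0.777 and 0.940 SD thresholds above apply to the interaction only; the adjusted contrast depends on the correlation between M0 and M1, which the plan does not give.
5. Report within-arm changes with CIs as descriptive, including any paired follow-up tests after a significant interaction. Do not use them as evidence of programme efficacy or to compare the arms.
6. Say which means Tukey's procedure compares, and drop it if it applies only to the two-level time factor.

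Cost: edits to the text, with no new patients or measurements. The sponsor gives up timing claims and within-arm efficacy claims, and relies on a between-arm contrast that is estimated less precisely than the overall change over time.
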